## **8.2 Secondary Outcome Analysis**

### **8.2.1 Key Secondary Endpoint Analysis**

The analysis of the key secondary endpoint will be formally conducted, once the primary endpoint is significant at a two-sided alpha of 0.05. Then a two-sided alpha of 0.05 will be applied to the primary analysis of the key secondary endpoint.

The key secondary endpoint of the trial is the annualized rate of eGFR change, which is derived from each individual subject's eGFR slope using the CKD-EPI formula. Slope is preferred as a practical and clinically meaningful endpoint. In this analysis, all eGFR observations from placebo run-in, tolvaptan run-in (not including tolvaptan titration), double-blind treatment, and post-treatment follow-up (not including data collected in the first week after the last IMP dose) periods will be included in the analysis, with the data of tolvaptan run-in and tolvaptan subjects in the double-blind treatment period are flagged (yes = 1 and no = 0) with a tolvaptan acute hemodynamic effect. The linear mixed effect model with effects of time (as a continuous variable), treatment, time-treatment interaction, acute hemodynamic effect, pre-treatment baseline (of the primary endpoint), and randomization stratification factors will be used to fit the GFR estimates, in which the intercept and time are both a fixed effect and a random effect. An unstructured variance covariance matrix is assumed for the random intercept and time. The time variable used in the model may start from the first observation of eGFR obtained from placebo run-in period. The covariate "acute hemodynamic effect" in the model is the flag variable with value of 0 and 1 specified earlier in this section for the data observed during tolvaptan run-in and the data observed for tolvaptan subjects during the double-blind treatment period. The starting point of this eGFR slope analysis is the eGFR observation during the placebo run-in period.

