3.6 Measures to Minimize/Avoid Bias

Only subjects who reach Day -1 and are who have indicated that they would likely be able to tolerate a dose of tolvaptan “for the rest of their lives” at a level of 60/30 mg or 90/30 mg will be eligible to enter the double-blind, randomized treatment period. In this

period, neither the subject nor the investigator or his/her staff will know which treatment is assigned. Immediately prior to randomization, and at all subsequent visits or site-subject contacts, the subject will be reminded of the importance of their commitment to continue participation in the trial, however the subject will not be told that this day is the point at which randomization to long-term therapy occurs.

Randomization will be 1:1, tolvaptan (60/30 mg or 90/30 mg) to placebo, and will utilize an interactive voice response system (IVRS) to ensure appropriate stratification.

Estimated GFR is an important predictor of the rate of renal function decline; therefore, subjects will be stratified by their baseline eGFR at a threshold of [REDACTED] and by age (≤ 55 or > 55 years old). Subjects will also be stratified by three TKV criteria [REDACTED].

The prescription of additional fluid to subjects in this trial may serve to confound subject unblinding, but it is acknowledged that, with a randomized withdrawal design, a limitation of the main and exploratory analyses might include the subject's perception of their treatment assignment. Note, however, that calculation of eGFR is an objective measure and is expected to be unaffected by such perceptions.

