### 8.3 Technical Computational Details for Primary and Secondary Analysis

(1) Two samples/aliquots of blood will be collected for serum creatinine assessments. While one blood sample will be analyzed by the central laboratory as soon as it is received and accessioned, the other one will be frozen and later batched analysis when a subject completes all his/her serum creatinine blood draws needed in the protocol. This batched assessment of serum creatinine is considered to have less intra-subject variation, and will be used for the eGFR derivations for the efficacy analysis. Since it is expected that two different methods are applied to these two sets of blood samples (enzymatic method to the batched sample and rate blank method to the first sample), these two sets of eGFR data are not interchangeable. In addition, the eGFR labeled as “Unscheduled” will be used in efficacy analysis if a subject has two eGFRs observed on the same day and same time.

██  
██  
██

[REDACTED]

Or

[REDACTED]

- (3) The following SAS codes will be used for the primary analyses:

```
PROC GLM;  
  CLASS TREATMENT AGE_STATUS GFR_STATUS TKV_STATUS;  
  WEIGHT WEIGHT;  
  MODEL ANNUALIZED_CHANGE = TREATMENT BASELINE AGE_STATUS  
                                GFR_STATUS TKV_STATUS;  
RUN;
```

- (4) The SAS code of the sensitivity analysis of the primary endpoint specified in [Section 8.1.2](#) is

```
PROC MIXED EMPRICAL;  
  CLASS SUBJECT TREATMENT AGE_STATUS GFR_STATUS TKV_STATUS;  
  MODEL GFR = TREATMENT TIME TREATMENT*TIME BASELINE  
              AGE_STATUS GFR_STATUS TKV_STATUS;  
  RANDOM INTERCEPT ITIME/TYPE=UN SUB=SUBJECT G;  
RUN;
```

If the model has any convergence problem, the variables of AGE\_STATUS, GFR\_STATUS, and TKV\_STATUS may be dropped out of the model.

- (5) The SAS code of the analysis of the key secondary endpoint specified in [Section 8.2.1](#) is

```
PROC MIXED EMPRICAL;  
  CLASS SUBJECT TREATMENT AGE_STATUS GFR_STATUS TKV_STATUS;  
  MODEL GFR = TREATMENT TIME TREATMENT*TIME BASELINE  
              ACUTE_HEMODYNAMIC_EFFECT AGE_STATUS GFR_STATUS  
              TKV_STATUS;  
  RANDOM INTERCEPT ITIME/TYPE=UN SUB=SUBJECT G;  
RUN;
```

If the model has any convergence problem, the variables of AGE\_STATUS, GFR\_STATUS, and TKV\_STATUS may be dropped out of the model.

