(6) The on-treatment visits included in the sensitivity analysis of the key secondary endpoint mentioned in Section 8.2.2 are Months [REDACTED]. The mean value of these visits in months is 6.5. For a new numerical axis with its original falling at 6.5 months, the 12 original time points will become [REDACTED] on this numerical axis. Thus the coefficients of the linear trend contrast of these 12 months are [REDACTED]. With treatment be coded, for example, as 0 for placebo and 1 for tolvaptan, the SAS code for the analysis of the key secondary endpoint is

```

PROC MIXED ;
  CLASS TREATMENT VISIT AGE_STATUS GFR_STATUS TKV_STATUS
  SUBJECT ;
  MODEL CHANGE = TREATMENT VISIT TREATMENT*VISIT BASELINE
  BASELINE*VISIT AGE_FACTOR GFR_FACTOR TKV_FACTOR ;
  REPEATED VISIT / TYPE=UN SUB=SUBJECT ;
  LSMEANS TREATMENT*VISIT / PDIFF CL ALPHA=0.05 ;
  ESTIMATE 'TREND DIFF' TREATMENT 0 0
  VISIT 0 0 0 0 0
  TREATMENT*VISIT [REDACTED]
  ;
RUN ;

```

If the estimate statement is not estimable, the fixed effects of AGE\_STATUS, GFR\_STATUS, and TKV\_STATUS may be dropped out of the model. In addition, 6/143 will be multiplied to the estimate of the linear trend contrast in order to provide an estimate of treatment difference in eGFR slope.

In case there is a convergence problem in the MMRM model with the unstructured variance covariance matrix, the following variance covariance matrix structures will be used in the order of 1) heterogeneous toeplitz, 2) heterogeneous autoregressive of order 1, 3) heterogeneous compound symmetry, 4) autoregressive of order 1, and 5) compound symmetry. The first (co)variance structure which does not have convergence problem will be the one used for the analysis. If a structured covariance has to be used, the “sandwich” estimator of the variance covariance matrix of the fixed effects parameters will be used in order to deal with possible model misspecification of the covariance matrix.

(7) For a tolvaptan subject who have IMP interruption during the trial, if the subject have eGFR observed during the interruption and the eGFR observation is more than one week from the last IMP dose before the interruption, the eGFR observation will be flagged (yes=1 and no = 0) with a tolvaptan hemodynamic effect and included in the key secondary analysis. If the observation is less than one week but more than 24 hours from

the last IMP dose before the interruption, the observation will be excluded from the key secondary analysis.

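### The key secondary slope model lets baseline eGFR and the stratification factors adjust the eGFR level but not the slope difference being tested; the cost is modest and the remedy cheap

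*SAP*

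**What the plan says.** SAP 8.2.1 fits a linear mixed model with "effects of time (as a continuous variable), treatment, time-treatment interaction, acute hemodynamic effect", and the list ends with baseline and the stratification factors: "acute hemodynamic effect, pre-treatment baseline (of the primary endpoint), and randomization stratification factors will be used to fit the GFR estimates". The random part is a model "in which the intercept and time are both a fixed effect and a random effect", with unstructured covariance. Protocol 7.4.2.1 gives the same list of effects.

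The SAS code in SAP 8.3(5) agrees. It begins "MODEL GFR = TREATMENT TIME TREATMENT*TIME BASELINE" and continues with "ACUTE_HEMODYNAMIC_EFFECT AGE_STATUS GFR_STATUS" and TKV_STATUS. TREATMENT*TIME is the only product with TIME. The sensitivity model for the primary endpoint (SAP 8.1.2, code in 8.3(4)) has the same structure without the hemodynamic flag.

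Three other places bear on this:

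- Protocol 3.6 gives the reason for stratifying: "Estimated GFR is an important predictor of the rate of renal function decline".
- The MMRM sensitivity analysis of the key secondary endpoint (SAP 8.2.2, code in 8.3(6)) carries "BASELINE*VISIT AGE_FACTOR GFR_FACTOR TKV_FACTOR". Baseline interacts with visit there, but the three strata do not.
- SAP 8.3(5) adds a fallback: "If the model has any convergence problem", the three stratum variables may be removed. By contrast, 8.3(6) handles non-convergence with an ordered list of covariance structures.

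**The concern.** A main effect in a model for eGFR moves a subject's fitted line up or down by the same amount at every visit. It cannot explain why one subject declines faster than another. Slope variation related to baseline eGFR, age or kidney volume therefore stays in the random slope and adds to the standard error of TREATMENT*TIME. If the arms differ by chance in baseline eGFR, the expected difference in slope from that imbalance goes straight into the estimated treatment effect.

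The primary weighted ANCOVA does not share the gap: its outcome is already an annualized change, so its main effects of baseline and strata do adjust a rate. The key secondary test is the second confirmatory test in the hierarchy and relies on data missing at random. That assumption is easier to defend when predictors of both slope and dropout act on the slope in the model.

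**Working it through.** **The plan's figure.** SAP 4.1 states 734 subjects for 90% power on the key secondary endpoint, two-sided 0.05, 1:1. The slope and residual variances behind it are redacted, so 734 cannot be reproduced independently. As a check of method on an unredacted figure, the primary endpoint (difference 1.07, variance 32.8, 90% power, 10% dropout) gives 2 × 603 = 1206, and 1206/0.9 = 1340, against 1336 stated.

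**Back-solving 734.** The assumed difference is 4.5 × 0.25 = 1.125 mL/min/1.73 m² per year. From n per arm = 2·SD²·(1.960 + 1.282)²/1.125² = 367, the implied SD of a per-subject slope estimate is 4.70 (variance 22.1). Power is then 98.4% with 1170 evaluable (1300 × 0.9) and 99.1% with 1300.

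**How strongly baseline predicts slope.** Table 1.2-1 of the protocol gives placebo slopes of -3.85 (stage 2, 60-90), -5.23 (stage 3a, 45-60) and -5.99 (stage 3b, 30-45). With band midpoints 75, 52.5 and 37.5:

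- stage 2 to 3a: 1.38/22.5 = 0.061 per year of slope per mL/min of baseline
- stage 3a to 3b: 0.76/15 = 0.051
- overall: 2.14/37.5 = 0.057

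Table 3 of the SAP's sample size memorandum gives a baseline SD of 11.45. Slope variance explained is (0.057 × 11.45)² ≈ 0.43, or about 0.4. As a share of an assumed slope variance, 0.4/28 = 1.4% and 0.4/8 = 5%.

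**Effect on sample size and power.** Treat the population as two equal halves whose slopes differ by a gap g, so that the explained variance is g²/4, and compare with 22.1.

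| Gap g per year | g²/4 | Share of 22.1 | N for 90% power | Power, 1170 evaluable |
|---|---|---|---|---|
| none modelled | – | – | 734 | 98.4% |
| 0.76 (3a vs 3b) | 0.144 | 0.7% | 730 | 98.4% |
| 2.14 (2 vs 3b) | 1.145 | 5.2% | 696 | 98.8% |

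The second gap is generous, because it applies the whole stage 2 to 3b distance to the two halves. Even an assumed 20% share gives power of 99.6%, a gain of 1.2 points.

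**Simulation, complete data.** 400 trials of 1170 subjects were generated on the protocol visit schedule with the hemodynamic flag, simple randomization and a true difference of 1.125.

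| Gap g | Model | Mean | SD | Change in estimate per unit imbalance in low-eGFR share |
|---|---|---|---|---|
| 0.76 | no covariates | 1.134 | 0.2554 | -0.76 |
| 0.76 | main effects (as planned) | 1.134 | 0.2554 | -0.76 |
| 0.76 | with covariate × time | 1.134 | 0.2555 | -0.02 |
| 2.14 | no covariates | 1.134 | 0.2556 | -2.14 |
| 2.14 | main effects (as planned) | 1.134 | 0.2556 | -2.14 |
| 2.14 | with covariate × time | 1.134 | 0.2486 | -0.02 |

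For the tested parameter the planned main effects do what no covariates would do. A separate simulation with a continuous baseline gradient gave variance savings of 4.4%, 1.4% and 0.7% for slope variances of 8, 16 and 28.05. With 400 trials, simulation noise is of the same order as these savings, so they mean a few percent at most.

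**Size of chance imbalance.** Under simple randomization one standard deviation of the arm difference in mean baseline is 11.45 × √(2/585) = 0.67 mL/min. Times 0.057 this is 0.04 per year in the slope difference, against a standard error near 0.26. Stratifying on eGFR reduces it further.

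**Dropout related to baseline.** The pattern is assumed: 25-30% dropout in low-eGFR tolvaptan subjects, 5% in high-eGFR tolvaptan subjects, 5-7.5% on placebo, gradient 0.05. The planned model averaged 1.136 to 1.155 and the model with baseline by time 1.119 to 1.122 (true 1.125). The gap is about 0.02 to 0.03 in tolvaptan's favour, under 0.2 standard errors. With a gradient of 0.10 it was 0.03 to 0.065; with 10% dropout in every group there was none.

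**The case against.** The strongest reply is that nothing here threatens validity. Treatment is randomized within these strata, the estimate is unbiased with complete data, and the code asks for empirical standard errors. The endpoint is already powered at about 98-99% on the implied SD. For the 0.76 gap the augmented model showed no gain at all. The gradient itself is soft: the stage 3b placebo slope rests on 14 subjects, and stage 2 lies mostly above this trial's eGFR ceiling of 65. Baseline by visit is already in the MMRM, subgroup analyses by these factors are planned, and changing a confirmatory model at SAP version 6 is more than an editorial edit.

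Most of this stands, and it keeps the point small. What it does not answer is that the planned covariates do nothing for the tested parameter, while the data needed to make them useful are already collected.

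Three stronger readings are tempting and not supported:

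- A reader might expect much larger savings once kidney volume and age also act on the slope. Neither document gives a slope by kidney volume or age, so no such figure can be defended.
- A reader might say the slope model contradicts the MMRM throughout. The mismatch holds for baseline only, since the MMRM also enters the strata as main effects.
- A reader might think the fallback of dropping the strata damages the test. With complete data those main effects barely touch the slope difference. The fair criticism is that the rule is discretionary and removes fixed effects before trying a simpler covariance.

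**Conclusion.** The point holds as a modest improvement in efficiency and robustness. It is not a flaw that invalidates the key secondary test. SAP 8.2.1, SAP 8.3(5) and Protocol 7.4.2.1 agree that baseline eGFR and the strata do not adjust the tested slope difference, which sits poorly with the protocol's own reason for stratifying. The variance and power figures rest on the earlier trial's stage-specific placebo slopes, an assumed slope variance of 8 to 28, and an SD back-solved from 734. Any bias in tolvaptan's favour needs dropout that depends on baseline eGFR differently by arm. The protocol reports early, imbalanced tolvaptan withdrawal in the earlier trial (Section 2.1), but not that it varied with baseline, so this remains a possibility and not a finding.

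**What to change.** Before unblinding, add BASELINE*TIME, AGE_STATUS*TIME, GFR_STATUS*TIME and TKV_STATUS*TIME to SAP 8.2.1 and 8.3(5), and likewise to 8.1.2 and 8.3(4). Keep the main effects, and centre the covariates so that the arm-specific slopes remain interpretable. This is five more fixed-effect parameters (one each for baseline, age and GFR, two for the three TKV categories) and needs no new data, visits or subjects.

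If the confirmatory specification is already locked, leave it and pre-specify the augmented model as a sensitivity analysis.

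Replace the convergence rule in 8.3(4) and 8.3(5) with a fixed order: rescale TIME first, then work through a stated list of covariance simplifications, as 8.3(6) does, and remove fixed effects only if those steps fail. The choice of structures can stay with the trial statisticians. A diagonal random-effect matrix is not an obvious default, since it forces a zero intercept-slope covariance and depends on where TIME is set to zero.

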### **8.2.2 Sensitivity Analysis of the Key Secondary Endpoint**

This sensitivity analysis of the key secondary endpoint of this trial is to compare the linear trend of eGFR between tolvaptan and placebo groups. The advantage of this sensitivity analysis is that it does not depend on the assumption of linearity and equal tolvaptan hemodynamic onset and offset effects used in [Section 8.2.1](#). The change from the pre-treatment baseline during the on-treatment visits in the double-blind treatment period will be included in the analysis. Since the hemodynamic effects of tolvaptan are believed to begin to reverse within 1 to 2 days, therefore on-treatment will be defined as within 24 hours of the last IMP dose.

Analysis of MMRM will be applied to the data of change from baseline in eGFR in Month 1, Month 2, ..., up to Month 12. The model will have fixed effect of treatment,

visit, treatment visit interaction, randomization stratification factors, and covariate baseline and baseline visit interaction. An unstructured variance-covariance matrix is assumed for the repeated measurements. A linear contrast of the treatment differences in these 12 months will be used as the sensitivity analysis of the key secondary endpoint.

Another sensitivity analysis will apply MMRM analysis similar to the one provided in the previous paragraph (without deriving linear contrast) to the data of change from baseline in eGFR, from Tolvaptan Titration Visit, Tolvaptan Run-in Visits 1 and 2, and Month 1, Month 2, ..., up to Month 12, and Post-treatment Follow-up Visit (average).

### **8.2.3 Sensitivity Analysis Including Data from Subjects Who Discontinue IMP**

This sensitivity analysis deviates from the MAR assumption to include the post-discontinuation follow-up data in the analysis of the key secondary endpoint. Subjects who discontinue treatment after randomization without withdrawing consent will be followed for additional eGFR (not including the eGFR observed in the 3 week period immediately post the last dose of IMP) up to Month 12. The data collected during this follow-up period will not be included in the key secondary endpoint analysis for the reasons given above. However, a sensitivity analysis including these follow-up data for the key secondary analysis will be performed. This analysis uses the same approach provided in the [Section 8.2.1](#) for the analysis of the key secondary endpoint.

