Renal impairment reduces tolvaptan clearance and consequently plasma concentrations increase. Following a single 60 mg dose, tolvaptan AUC in subjects with ██████████ higher compared to subjects with ██████████. Tolvaptan is highly bound to plasma proteins (> 98%) and binding was unaffected by renal impairment.

Pharmacodynamic (PD) responses to tolvaptan were observed for subjects with ADPKD at CKD stages 1 to 4. At the recommended split-dose regimens of 45/15 mg to 90/30 mg daily, tolvaptan blocked AVP action at the V_2 receptor (ie, increased urine excretion rates and suppressed U_{osm}) for almost the entire 24-hour day in subjects with ADPKD (CKD Stage 1 to 2). The large increase in urine output that resulted from this inhibition was associated with the 5 most frequently reported adverse events (AEs; polyuria, pollakiuria, nocturia, thirst, and dry mouth) in clinical pharmacology or clinical efficacy trials. In 2 clinical pharmacology trials in subjects with ADPKD and estimated glomerular filtration rates (eGFR) > 60 mL/min/1.73m² administered a 90/30 mg dose regimen for at least 7 days, mean (standard deviation [SD]) 24-hour urine volumes were 7.464 (2.103) L and 6.532 (2.036) L. As renal function declined, the volume of urine produced for a given dose of tolvaptan decreased; following a 90/30 mg split-dose regimen, mean (SD) 24-hour urine volumes for subjects with ADPKD and eGFR 30 to 60 and < 30 mL/min/1.73m² were 6.233 (1.307) L and 5.024 (1.767) L, respectively. Therefore, despite an increase in tolvaptan concentration, the clinical effects of tolvaptan on the most common adverse events are diminished. Other adverse reactions, such as idiopathic liver injury, do not appear to be concentration-dependent.

Subjects with ADPKD are able to maintain a neutral fluid balance so increases in serum sodium and plasma osmolality were small, following tolvaptan treatment. Serum concentrations of creatinine, cystatin C, and uric acid were higher following tolvaptan treatment as tolvaptan reduced the eGFR approximately 6 to 8%, CrCL approximately 8 to 10%, and uric acid clearance approximately 20 to 25%; the changes appeared to

independent of baseline renal function for CKD stages 1 to 4. Urinary excretion of aquaporin 2 and cAMP were lower following tolvaptan treatment, supporting the hypothesis that tolvaptan inhibition of the V₂ receptor is successful in reducing cellular cAMP concentrations.

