## **8 Efficacy Analysis**

### **8.1 Primary Outcome Analysis**

This trial's estimand is the difference in outcome improvement if all subjects tolerated and adhered to their treatment. To enrich this population, only subjects that can tolerate the tolvaptan titration and run-in periods will be randomized. This approach combines estimands #2 and #3 recommended by the 2010 National Academy of Sciences' National Research Council report on prevention and treatment of missing data. Thus, data MAR is assumed in the primary analysis. Sensitivity analysis will be provided to address the concern of data MNAR.

This estimand focuses on the efficacy of tolvaptan in slowing renal function decline. The objective of this trial is to confirm a causal effect of tolvaptan in slowing renal function decline, consistent with the selection of an efficacy rather than effectiveness estimand.

An effectiveness estimand compares treatment policies and reasonably could include data acquired long after withdrawal from the trial (eg, when subjects discontinue tolvaptan but are followed for many weeks or months) or move to an alternate treatment regimen (eg, placebo subjects being prescribed commercial tolvaptan upon approval for ADPKD). In the absence of an approved and effective alternate treatment for ADPKD; it is premature to discuss treatment policies. Thus, while eGFR data collected in the second and third week post withdrawal are used for analysis of the primary endpoint, data collected long after withdrawal or after a subject moves to an alternate treatment regimen will be excluded in the primary analyses of both the primary and the key secondary endpoints.

Proposed tables and figures to be generated for the efficacy analysis can be found in [Appendix 3](#) and [Appendix 4](#).

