### **8.1.3 Sensitivity Analysis Including Data from Subjects Who Discontinue IMP**

The sensitivity analysis deviates from the MAR assumption to include the post-discontinuation follow-up data in the analysis specified in the section of the primary analysis. Subjects who discontinue treatment after randomization without withdrawing consent will also be followed for additional off-treatment eGFR values up to Month 12. These post “post-treatment follow-up” eGFR data at Month 12 will be included to replace the data observed during post-treatment follow-up for the subjects who discontinue IMP early in a sensitivity analysis using the same analytic approach specified in the section of the primary analysis.

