will be mapped to visit Month 12. If an unscheduled visit or an end of treatment visit is more than 2 days post last dose, it will not be mapped to these double-blind nominal visits, but will be considered for the post-treatment follow-up visits, if it falls within 7 to 40 days from the last dose of IMP.

(12) The following reasons are collected in the CRF for subjects who discontinue IMP:

1. Discontinued based on subject decision:
  - 1.1. IMP not tolerable (AE which is annoying or uncomfortable but not serious or hazardous)
  - 1.2. Reason other than tolerability
    - 1.2.1. Pregnancy
    - 1.2.2. Trial too burdensome
    - 1.2.3. Other reason
  - 1.3. Taking marketed product for tolvaptan
2. Discontinued based on physician decision
  - 2.1. Potential IMP-related safety concern or serious AR placing subject at undue hazard
  - 2.2. Progression of disease leading to dialysis, transplantation or eGFR decline
  - 2.3. Hepatic AE
3. Other
  - 3.1. Subject death
  - 3.2. Subject lost to follow-up

In [Section 8.2.4](#) for sensitivity analysis including imputation of missing data, six reasons of discontinuation of IMP were listed in the order of their likelihood to be MNAR. The mapping of the reasons of discontinuation of IMP to the reasons used in the sensitivity analysis is provided below:

- Progression of renal disease or Lack of efficacy: Item 2.2
- Other AE: Items of 1.2.3, 2.1, 2.3, 3.1 and 3.2
- Aquaretic AE: Item 1.1
- Trial too burdensome: Items of 1.2.1 and 1.2.2
- Commercial tolvaptan for ADPKD available: Item 1.3

The reason to map Items of 1.2.3 (Other reasons under Reason other than tolerability) and 3.2 (Subject lost to follow-up) to other AE is for conservativeness to consider them as a reason to be more likely MNAR.

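### In SAP 8.2.3 a placebo subject taking marketed tolvaptan carries hemodynamic flag 0, so a reversible eGFR drop is fitted as decline; in 8.1.3 the same drop enters a switcher's Month 12 value unadjusted in either arm

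*SAP*

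**What the plan says.** **Switching is foreseen.** SAP 8.3 item 12 lists "Taking marketed product for tolvaptan" among the reasons for stopping IMP, as does Protocol 3.8.3.4. SAP 8.1 itself gives the example of placebo subjects who are prescribed the commercial product.

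**Switchers stay under observation.** Protocol 3.7.1.2 and 3.8.3.3 keep subjects who stop IMP on monthly visits to Month 12. Protocol 5.6 continues to collect their creatinine and concomitant medications.

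**The exclusion is limited.** SAP 8.1 says that "data collected long after withdrawal or after a subject moves to an alternate treatment regimen will be excluded in the primary analyses" of the two endpoints; Protocol 7.4 agrees. SAP 8.1.3 and 8.2.3 do not repeat this exclusion.

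**SAP 8.2.3** adds the later data ("However, a sensitivity analysis including these follow-up data for the key secondary analysis will be performed") and keeps the model: "This analysis uses the same approach provided in the" key secondary section, 8.2.1. That section sets the flag "with the data of tolvaptan run-in and tolvaptan subjects in the double-blind treatment period are flagged (yes = 1 and no = 0"), and defines it again for data from "tolvaptan run-in and the data observed for tolvaptan subjects during the double-blind treatment period".

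**SAP 8.1.3** says that "eGFR data at Month 12 will be included to replace the data observed during post-treatment follow-up for the subjects who discontinue" IMP early, and reuses the primary weighted ANCOVA. The code in SAP 8.3 item 3 contains treatment, baseline and the three stratification factors, with no hemodynamic term.

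SAP 8.3 item 7 has a rule for IMP interruptions in tolvaptan subjects. No item covers marketed product.

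**The concern.** The acute effect of tolvaptan on eGFR reverses when the drug stops (Protocol 2.1). The primary endpoint avoids it by comparing off-drug with off-drug values, and the key secondary model removes it with the flag. Protocol 7.4.1.2 bars unadjusted on-tolvaptan data from its own sensitivity analysis. An eGFR value on marketed tolvaptan carries the same effect, but nothing in 8.1.3 or 8.2.3 removes it.

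In 8.2.3 a placebo switcher's late values sit lower with flag 0, so the model can only read the step down as faster placebo decline. In 8.1.3 the step is annualized as if it were lost function. Keeping data after a switch can be defended for a treatment-policy question, but treating a reversible drug effect as lost kidney function cannot.

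These two analyses are the plan's stated departures from MAR that use observed data after IMP is stopped. If they are distorted, they are a poor guide to whether the main result survives informative stopping. The 8.2.4 set built on the 8.2.3 data is affected as well.

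**Working it through.** **1. Yardstick.** The plan gives no figure for switching, so the planned effect of 1.07 is the comparison. It reproduces the plan's sample size. With three draws the variance is 28.05 + 2 × 7.1/3 = 32.78. Two-sided 0.05 and 90% power give 602 per arm, 1204 in total, and 1204/0.9 = 1338, against 1336 in SAP 4.1.

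**2. Acute drop.** Protocol 1.3 reports that "tolvaptan reduced the eGFR approximately 6 to 8" percent. At the mean baseline of 43.21 (SAP Appendix 5, Table 3) that is 0.06 × 43.21 = 2.59 to 0.08 × 43.21 = 3.46. The same table shows mean changes of -3.65 at titration and -3.21 and -3.40 at run-in.

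**3. SAP 8.1.3.** Shift in the placebo mean = share switching × drop / duration. The drop runs from 2.59 to 3.65. Duration runs from 1.000 to 1 + 6/52 = 1.115 years, because baseline lies about six weeks before randomization.

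| Placebo share switching (assumed) | Lowest | Highest |
|---|---|---|
| 2% | 0.02 × 2.59/1.115 = 0.046 | 0.02 × 3.65/1.000 = 0.073 |
| 5% | 0.116 | 0.182 |
| 10% | 0.232 | 0.365 |

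These figures leave out any slowing of decline on the marketed drug. If both arms switch equally the drop cancels, because the model treats the arms alike. At a drop of 3.40, creating a difference of 1.07 from nothing would need a net placebo excess of 1.07/(3.40/1.115) = 35%.

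**4. SAP 8.2.3.** Expected values of the 8.2.1 model were fitted by generalized least squares (intercept, arm, time, arm × time, flag; random intercept and slope). Baseline and stratification covariates were left out. The true slopes are -4.5 (SAP 4.1) and -3.43, a difference of 1.07, and the drop is 3.4. Assumptions: random-effect variances 30 and 8; residual variance 7.1; three off-drug samples after IMP stop, then marketed tolvaptan to Month 12; placebo switchers then decline at the tolvaptan rate. With 5% of placebo and no tolvaptan subjects switching:

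| IMP stopped at | Flag as written | Flag by actual exposure | Inflation |
|---|---|---|---|
| Month 3 | 1.233 | 1.034 | 0.199 |
| Month 6 | 1.217 | 1.051 | 0.166 |
| Month 9 | 1.142 | 1.065 | 0.077 |

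The exposure-based value falls slightly below 1.07 because switchers truly slow down, which is a real effect. The inflation is 0.031 to 0.080 at 2% switching and 0.155 to 0.399 at 10%.

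**5. Direction by arm.** The flag for a tolvaptan-arm subject after permanent IMP stop is undefined. Read literally as ending with IMP, it becomes 0. Protocol 3.10 defines the treatment period without regard to whether all doses are taken, so a reader could hold it at 1 to Month 12. With IMP stopped at Month 6:

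| Who switches | Flag 0 after IMP stop | Flag held at 1, tolvaptan arm | Flag by exposure |
|---|---|---|---|
| 5% placebo only | 1.217 | 1.217 | 1.051 |
| 5% in each arm | 1.050 | 1.217 | 1.050 |
| 5% tolvaptan only | 0.903 | 1.070 | 1.070 |

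**The case against.** The strongest reply has four parts.

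- **The plan is silent.** Neither section mentions marketed tolvaptan, so retention of these values is inferred from the missing exclusion. SAP 8.1.3 also calls its added values off-treatment. This stands as a caution, but the titles of tables CT-1.2.3.1 and CT-1.2.3.2 use that term for results after study medication is stopped. If 8.1.3 meant off all tolvaptan, it would still need to say what replaces a switcher's Month 12 value.
- **Direction.** A reader might infer that both analyses favor tolvaptan because the flag follows the randomized arm. The documents do not support that. SAP 8.1.3 has no flag, switching is a listed reason in both arms, and no rates are given. This part stands in full.
- **Less conservative than the main analysis?** A reader might infer this too, but it is not shown. The same analyses also pick up tolvaptan subjects who stop and lose benefit. If 10% stop halfway and then decline at the placebo rate, the difference shrinks by 0.10 × 0.5 × 1.125 = 0.056 per year (1.125 is 25% of 4.5), close to the effect of 2% placebo switching. The net sign is therefore unknown. But loss of benefit is what these analyses exist to show, and an artifact of similar size can hide it.
- **Limited reach.** Planned dropout for all reasons is 10%, so 10% switching in placebo is strained. The on-treatment MMRM in 8.2.2 and the 8.2.4 set built on 8.2.1 data are unaffected. This stands and limits the weight of the point.

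**Conclusion.** The point holds for SAP 8.2.3 and for the 8.2.4 imputation set built on its data. Followed literally, the flag rule gives a placebo subject on marketed tolvaptan flag 0 and fits the acute drop as decline. In 8.1.3 the problem is a different one: there is no hemodynamic term, so a Month 12 value on marketed tolvaptan enters unadjusted in either arm.

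If 5% of placebo subjects and no tolvaptan subjects switch, the 8.2.3 slope difference is inflated by about 0.08 to 0.20 per year (7 to 19% of 1.07). The 8.1.3 difference shifts by about 0.12 to 0.18 per year. Both favor tolvaptan. Mainly tolvaptan-arm switching works against tolvaptan in 8.1.3, and in 8.2.3 if the flag is 0 after IMP stops. Equal switching cancels under the same conditions; if the flag stays at 1 for the tolvaptan arm to Month 12, the inflation in 8.2.3 remains. Switching rates, switch times and the random-effect variances are assumptions.

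It would be wrong to infer that the confirmatory results are biased: SAP 8.1 removes post-switch data from the primary analyses of both endpoints. The point is worth fixing because the correction is cheap and the result should not depend on an undefined flag.

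**What to change.** - **SAP 8.2.3, and the 8.2.4 set that uses its data:** set the hemodynamic flag by actual tolvaptan exposure at the time of the sample, from IMP or marketed product, in either arm, including after IMP is stopped.
- **SAP 8.1.3:** do not use a Month 12 value taken on marketed tolvaptan as the replacement. Use the last off-drug value before the switch, or the post-treatment follow-up mean if there is none.
- **Reporting:** give the number of switchers by arm.

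The cost is a few sentences in the SAP and one derived variable from concomitant medication data that are already collected. The downside is that a few Month 12 values are not used in 8.1.3, and a switcher with no later off-drug value returns to the value used in the primary analysis.
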